3.5.2 Secondary Efficacy Endpoint and Analyses

3.5.2.1 Secondary Efficacy Endpoint

The secondary efficacy endpoint is the incidence of RSV LRTI hospitalization through 150 days post dose. For subjects with multiple RSV LRTI hospitalizations, only the first occurrence will be used in the analysis.

The events of “RSV hospitalization” are a subset of “medically attended RSV LRTI,” which are determined based on objective clinical LRTI criteria (described in the Protocol [Section 4.3.1.1](#) and SAP [Appendix 1](#)) and RSV test results obtained from central laboratory analysis respiratory secretions using a validated RSV reverse transcriptase -polymerase chain reaction (RT-PCR) assay for the detection of RSV A or RSV B.

Prior to analysis, a blinded review of data will be undertaken to determine an analysis window such that all positive results will be counted as an RSV LRTI hospitalization if they occurred in a respiratory sample collected within this window relative to the admission/deterioration date. The actual window used will be documented prior to unblinding. In addition, deaths that can be demonstrated as caused by RSV (by autopsy or clinical history and virologic evidence) will also be considered as RSV LRTI hospitalization endpoints.

3.5.2.2 Secondary Efficacy Analyses

A Poisson regression model with robust variance ([Zou, 2004](#)) using only the treatment term will be used to assess the treatment effect on the incidence of RSV LRTI hospitalization

between MEDI8897 and placebo groups in the ITT population. Relative risk reduction and its corresponding 95% CI are estimated from the model implemented by PROC GENMOD as detailed in Section 3.5.1.2.

Statistical testing of the null hypothesis that the incidence of RSV LRTI hospitalization between MEDI8897 and placebo groups is the same will only be performed if the primary efficacy analysis has achieved a p-value that is ≤ 0.05 . In that event, statistically significant treatment effect on this secondary efficacy endpoint will be claimed if the 2-sided p-value is ≤ 0.05 . In this approach, the family-wise Type I error rate of testing the first and the secondary efficacy hypotheses is controlled under the significance level of $\alpha \leq 0.05$.

Above stated analysis on RSV LRTI hospitalization will also be conducted on the per-protocol population.

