4.6 Treatment Assignment and Blinding

4.6.1 Methods for Assigning Treatment Groups

An IWRS will be used for randomization to a treatment group and assignment of blinded investigational product kit numbers. A subject is considered randomized into the study when the investigator notifies the IWRS that the subject meets eligibility criteria and the IWRS provides the assignment of blinded investigational product kit numbers to the subject.

Subjects will be randomized at a 2:1 ratio to receive a ■ mg IM dose of MEDI8897 (N = 1,000) or placebo (N = 500). Randomization will be stratified by temperate zones in the northern and southern hemisphere and by subject age at the time of randomization (ie, ≤ 3 months, $> 3 - \leq 6$ months, > 6 months). Enrollment of infants > 6 months of age will be limited to approximately 500.

The procedure for using IWRS is as follows:

- The investigator or designee contacts the IWRS and provides the SID number and subject's baseline characteristic(s) used to verify that it is the same subject
- Placebo (provided by site) or a vial from a MEDI8897 kit will be assigned to the subject
- Confirmation of this information is sent to the unblinded investigational product manager who prepares the investigational product to be dispensed to the subject per the response system and records the appropriate information in the investigational product accountability log

Investigational product (MEDI8897 or placebo) must be administered the same day the investigational product is assigned. Total in-use storage time from needle puncture of the investigational product vial to administration should not exceed 4 hours at room temperature. If storage time exceeds these limits, a new vial should be used. If there is a delay in the administration of investigational product such that it will not be administered within the specified timeframe, the unblinded investigational product monitor must be notified immediately.

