4.8.3.1 Primary Efficacy Analysis

The incidence of RSV LRTI (inpatient and outpatient) during 5 months of the RSV season will be based on RSV test results (performed centrally via RT-PCR) and objective clinical LRTI criteria and will be summarized by treatment group. For subjects with multiple medically attended RSV LRTI events, only the first occurrence will be used in the primary analysis.

The primary efficacy analysis of the primary endpoint will be conducted with the ITT Population. LRTI caused by RSV that occurs prior to discontinuation from participation in the study will contribute to the primary efficacy analysis. For subjects who do not have an RSV LRTI prior to discontinuation from participation, their event status will be imputed assuming the observed placebo RSV LRTI rate. This will be implemented by imputations based on repeated simulations and will be described in the Statistical Analysis Plan. A Poisson regression model with robust variance (Zou, 2004) will be used as the primary

efficacy analysis model to compare the incidence of medically attended RSV LRTI between MEDI8897 and placebo, including treatment group, age at the time of randomization (ie, ≤ 3 months, $> 3 - \leq 6$ months, > 6 months) and dichotomous temperate (northern and southern) hemispheres as covariates. In addition, the 2-sided p-value and corresponding 2-sided 95.1% CI on the relative risk will be provided from the model. Relative risk reduction is defined as $(1 - P_n/P_s)$ where P_n is the incidence of RSV LRTI during 5 months of the RSV season in the MEDI8897 group and P_s is the incidence of RSV LRTI during 5 months of the RSV season in the placebo group generated from the model. Statistical significance will be achieved if the 2-sided p-value is ≤ 0.05 .

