4.8.3.3 Secondary Efficacy Analyses

The incidence of RSV hospitalization during 5 months of the RSV season will be summarized by treatment group. The same methods described above for the primary efficacy endpoint will be used to assess treatment effect on RSV hospitalization. Following a hierarchical testing procedure, the secondary efficacy endpoint will be tested at the significance level of 2-sided 0.05 if the primary analysis on the primary efficacy endpoint has achieved statistical significance at the level of 2-sided 0.05.

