3.5.2.3 Handling of Dropouts and Missing Data

RSV LRTI hospitalization that occurs through 150 days post dose will contribute to the analysis. For subjects who do not have an RSV LRTI and were not followed through 150 days post dose, their event status will be imputed using the observed placebo RSV LRTI hospitalization rate following the repeated imputation procedure without involvement of stratification factors. The computation steps are similar to what has been described in the Sensitivity analysis 2 for the primary efficacy endpoint (Section 3.5.1.6).

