3.5.2.4 Additional Analyses of the Secondary Efficacy Endpoint

The additional analyses, including the CMH test with the only term of treatment for the incidence of RSV LRTI hospitalization, and the Kaplan-Meier for time-to-first RSV LRTI hospitalization will be conducted. Treatment effect for time-to-first RSV hospitalization will be tested by a log-rank test.

For each treatment group, age at onset of the first medically attended RSV LRTI hospitalization will be tabulated by age group used for randomization stratification by treatment group. In addition, time-to-first medically attended RSV LRTI hospitalization will be plotted at subject's level along the axis of age at birth. RSV hospitalization will also be summarized by RSV subtype (A or B).

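### The alpha-controlled RSV hospitalization test is specified differently in the protocol and SAP v5, and its imputation rule leaves one group of dropouts unclassified

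*SAP*

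**What the plan says.** **Design.** Protocol 4.6.1: "Randomization will be stratified by temperate zones in the northern and southern hemisphere and by subject age at the time of randomization". That gives two hemispheres by three age groups.

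**Primary model.** Protocol 4.8.3.1 specifies Poisson regression with robust variance, with treatment, age group "and dichotomous temperate (northern and southern) hemispheres as covariates". SAP v5 section 3.5.1.2 has the same terms, and 3.5.1.3 imputes dropouts at the placebo rate conditional on the strata.

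**Secondary endpoint, protocol.** Section 4.8.3.3: "The same methods described above for the primary efficacy endpoint will be used to assess treatment effect on RSV hospitalization". The synopsis says the same. The endpoint is tested at 2-sided 0.05 once the primary test succeeds.

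**Secondary endpoint, SAP v5.**
- Section 3.5.2.2: a robust Poisson model "using only the treatment term will be used to assess the treatment effect on the incidence of RSV LRTI hospitalization".
- Section 3.5.2.3: "For subjects who do not have an RSV LRTI and were not followed through 150 days post dose, their event status will be imputed" at the observed placebo hospitalization rate, "without involvement of stratification factors". The steps are said to be similar to those of sensitivity analysis 2 in section 3.5.1.6.
- Section 3.5.2.4: supportive analyses include "the CMH test with the only term of treatment for the incidence of RSV LRTI hospitalization", and a log-rank test for which no strata are named.
- Section 3.5.2.1: RSV hospitalizations are a subset of medically attended RSV LRTI.

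**The concern.** Hospitalization is the only secondary efficacy endpoint under the type I error hierarchy, so its p-value should follow from one unambiguous recipe. Three features of the current text prevent that.

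First, the protocol names the covariates, through its reference to the primary method, and the SAP removes them without giving a reason. Protocol Amendment 1 lists no change to this rule.

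Second, SAP v5 does not agree with itself. The procedure that 3.5.2.3 points to ends in a model with both stratification factors, whereas 3.5.2.2 has neither. That procedure also imputes at twice the placebo rate, whereas 3.5.2.3 speaks of the observed placebo rate. The word similar does not settle which parts carry over, so two programmers could produce different confirmatory p-values.

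Third, the condition for imputation is the wrong event. An infant who had an outpatient RSV LRTI and then left the study before 150 days without being hospitalized has an unknown hospitalization status. That infant did have an RSV LRTI, so falls outside the rule.

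**Working it through.** **1. The plan's own figure.** Power is stated only for the primary endpoint: about 99% in Protocol 4.8.2, above 99% in SAP 2.4. The inputs are 500 placebo and 1,000 MEDI8897 infants, an 8% placebo rate, a 70% reduction (2.4%) and 2-sided alpha 0.05.

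SE(log RR) = sqrt[(1−p0)/(n0·p0) + (1−p1)/(n1·p1)] = sqrt(0.92/40 + 0.976/24) = sqrt(0.0637) = 0.252. Then |log 0.3|/SE = 1.204/0.252 = 4.77, and power = Φ(4.77 − 1.96) = 99.75%. The stated figure reproduces.

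**2. The same formula for hospitalization.** The documents give no placebo hospitalization rate, so it is assumed. With a 70% reduction, treatment-only power is 65%, 82%, 92% and 96% at placebo rates of 2%, 3%, 4% and 5%. At 3%: SE = sqrt(0.97/15 + 0.991/9) = 0.418, z = 2.88, power = Φ(0.92) = 82%.

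**3. Effect of leaving out the strata.** 3,000 trials per scenario were simulated (1,500 infants, stratified 2:1), comparing the treatment-only robust Poisson model with the model adding age group and hemisphere. The documents give no strata effects, so these are assumed too. Results at a 70% reduction:

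| Placebo rate | Risk ratios by age; by hemisphere | SE, unadjusted/adjusted | Power, unadjusted vs adjusted | Tests disagree | Adjusted model not fitted |
|---|---|---|---|---|---|
| 3% | 1:1:1; 1 | 1.001 | 82.2% vs 82.3% | 0.0% | 6 |
| 3% | 2:1.5:1; 1.5 | 1.002 | 83.5% vs 83.6% | 0.1% | 12 |
| 3% | 4:2:1; 2 | 1.005 | 83.4% vs 84.2% | 0.7% | 100 |
| 4% | 1:1:1; 1 | 1.001 | 91.3% vs 91.3% | 0.0% | 1 |
| 4% | 2:1.5:1; 1.5 | 1.002 | 92.2% vs 92.2% | 0.0% | 1 |
| 4% | 4:2:1; 2 | 1.006 | 92.2% vs 92.5% | 0.2% | 31 |

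Across these scenarios and those with no effect or a 50% reduction, the SE ratio runs from 1.001 to 1.010. Under no effect, rejection is 4.1% to 5.0% for the treatment-only test and 4.0% to 5.0% for the adjusted test, with a Monte Carlo standard error of about sqrt(0.05 × 0.95/3,000) = 0.4 points. Adjusted power is computed over the trials in which that model fitted, so part of the largest gap (0.8 points) may reflect the 100 excluded trials. Those are 100/3,000 = 3.3% of that scenario.

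**4. Size of the imputation gap.** Under the design, 500 × 8% = 40 placebo and 1,000 × 2.4% = 24 MEDI8897 infants have an RSV LRTI. Let h be the share of these who are hospitalized and d the dropout share among the rest; both are assumed. Infants left out = (40 + 24)(1 − h)d.
- h = 75%, d = 2%: 64 × 0.25 × 0.02 = 0.3 infants.
- h = 25%, d = 10%: 64 × 0.75 × 0.10 = 4.8 infants.

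Multiplying by the implied placebo hospitalization rate, 0.08h, gives the imputed hospitalizations forgone: 0.02 to 0.13 over the range tried. The maximum is at h = 50%, d = 10%: 3.2 × 0.04 = 0.128.

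**The case against.** The strongest defence has four parts.

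*The treatment-only test is valid and nothing material is lost.* This stands. A reader might infer that ignoring the randomization factors makes the test materially conservative or underpowered. The documents do not support that. At 3% to 4% both tests hold close to 5%. A much higher hospitalization rate would exceed the 8% the design assumes for the whole primary endpoint, of which hospitalizations are a subset. The 11.3% quoted in the sample-size section comes from another trial in a different population.

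*Hospitalizations may be too few for covariates.* This is a fair reason, and the working shows that the adjusted model can fail. But it appears only in superseded SAP versions, and there about the imputation. SAP v5 does not give it. A pre-specified fallback answers it, as v5 already does for the primary model (3.5.1.2) and the subgroup models (3.5.1.7).

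*The protocol leaves details to the SAP.* It does, in 4.8.1, but the covariates are named in the protocol's own method, so removing them is a change to that method. The supportive CMH and log-rank tests are different: they carry no alpha, and leaving them unstratified does not touch the confirmatory claim.

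*The imputation wording is a slip.* Probably so, since SAP v3 conditioned on RSV LRTI hospitalization. It is still the operative text. A reader might also infer that the plan counts the skipped infants as not hospitalized. Section 3.5.2.3 does not say that. A non-event is the likely programming default, but a missing outcome that drops the infant from the model is another possible reading.

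**Conclusion.** The point holds as one of consistency and pre-specification. Protocol 4.8.3.3 and SAP v5 3.5.2.2 prescribe different models for a test that carries alpha. SAP v5 3.5.2.3 points to steps that contradict 3.5.2.2 on covariates and its own text on the imputation rate. Its condition, "For subjects who do not have an RSV LRTI and were not followed through 150 days post dose", leaves infants with an outpatient RSV LRTI and incomplete follow-up without a rule.

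The expected numerical effect is small: a standard error 0.1% to 1.0% larger, a power difference below 1 point, at most 0.7% of trials in which the two tests disagree, and about 0 to 5 infants outside the imputation. These figures rest on assumed placebo hospitalization rates of 3% to 4%, strata risk ratios up to 4:2:1 by age and 2:1 by hemisphere, 25% to 75% of RSV LRTIs hospitalized, and 2% to 10% dropout. The documents supply none of these. The simulation covers the analysis model only. It does not test stratified imputation with few events.

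**What to change.** - **3.5.2.2:** fit treatment, age group and hemisphere, as the protocol says. Add one fixed fallback for non-convergence, for example the stratified CMH already named as the primary fallback, or the treatment-only model. State how it works with the imputed datasets, because the CMH analysis in 3.5.1.4 currently runs without imputation. If the sponsor prefers the treatment-only model because events are few, Protocol 4.8.3.3 should be amended to say so and why.
- **3.5.2.3:** make the condition the absence of an RSV LRTI hospitalization together with follow-up that stops before 150 days. State the one-times placebo hospitalization rate and the analysis model in full, and remove the reference to sensitivity analysis 2. Unstratified imputation may stay if events are too few for strata, with that reason written down.
- **3.5.2.4:** stratifying the supportive CMH and log-rank tests is optional.

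The cost is SAP wording and little programming, since the stratified model and imputation steps are already specified for the primary endpoint. The one real risk is non-convergence with sparse events (up to about 3% of simulated trials), which the fallback covers.

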3.5.2.3 Handling of Dropouts and Missing Data

RSV LRTI hospitalization that occurs through 150 days post dose will contribute to the analysis. For subjects who do not have an RSV LRTI and were not followed through 150 days post dose, their event status will be imputed using the observed placebo RSV LRTI hospitalization rate following the repeated imputation procedure without involvement of stratification factors. The computation steps are similar to what has been described in the Sensitivity analysis 2 for the primary efficacy endpoint (Section 3.5.1.6).

3.5.2.4 Additional Analyses of the Secondary Efficacy Endpoint

The additional analyses, including the CMH test with the only term of treatment for the incidence of RSV LRTI hospitalization, and the Kaplan-Meier for time-to-first RSV LRTI hospitalization will be conducted. Treatment effect for time-to-first RSV hospitalization will be tested by a log-rank test.

For each treatment group, age at onset of the first medically attended RSV LRTI hospitalization will be tabulated by age group used for randomization stratification by treatment group. In addition, time-to-first medically attended RSV LRTI hospitalization will be plotted at subject's level along the axis of age at birth. RSV hospitalization will also be summarized by RSV subtype (A or B).

3.5.2.5 Subgroup Analyses for the Secondary Efficacy Endpoint

The incidence of RSV LRTI hospitalization will be summarized by the following subgroups.

- Hemisphere
- Country
- Age at randomization stratum (age \leq 3 months, age $>$ 3 to \leq 6 months, age $>$ 6 months)
- Gender
- Race (Caucasian, non-Caucasian)
- Weight at birth (weight \leq 2.5 kg, weight $>$ 2.5 kg)
- Weight on Day 1 (weight \leq 2.5 kg, weight $>$ 2.5 to \leq 5 kg, weight $>$ 5 kg)
- GA (29-32 weeks, $>$ 32 weeks)
- Sibling also participating in the study (yes/no)

3.5.3 Other Efficacy Analyses

An overall summary of subjects with any medically attended LRTI or hospitalization due to any respiratory illness will be presented by treatment group. Summary of medically attended LRTI, breaking done by protocol-defined LRTI (RSV or non-RSV) and non-protocol defined LRTI (RSV or non-RSV) with each further breaking done by hospitalization status, will be presented. In this summary, a subject is reported only once even he or she might have multiple LRTI events in the time interval of reporting. In that occasion, the event with the highest severity level will be reported. The rules to define severity among multiple LRTI events for a subject are as follows: Protocol-defined $>$ Non-protocol defined, RSV $>$ non-RSV, and Hospitalization $>$ non-Hospitalization. For subjects who were hospitalized due to any respiratory illness, non-LRTI cases will be further reported and broken done by RSV status. A subject is reported only once even he or she might have multiple non-LRTI events in the time interval of reporting. In that occasion the rule to report is RSV $>$ non-RSV.

For all medically attended LRTI, RSV status (positive, negative or not done) will be summarized by RT-PCR or local testing results by treatment group. The proportion of each category will be calculated based on the total number of LRTI events for the respective treatment group. In addition, incidence of positive RSV LRTI either by RT-PCR or by local testing results will also be summarized by treatment group. The same analysis window as described in above sections for the RT-PCR central tests will be used for the local tests. In this summary, only first occurrence of RSV LRTI event either by PT-PCR or local testing will be reported and the incidence of the event will be calculated based on the number of randomized subjects for the respective treatment group.

In addition, for each treatment group, all LRTI events will be tabulated by Inpatient (primary hospitalization, nosocomial hospitalization) and Outpatient, for the latter category, further presentation will be made by different medical settings: outpatient clinic, urgent care clinic, and emergency department visits. The proportion of each category will be calculated based on the total number of LRTI events for the respective treatment group.

All above stated summaries will be based on observed events and data summary will be presented by Day 150 post dose (on the ITT population), after 150 days post dose (on the ITT population with Day 151 visit), and through 360 days post dose (on ITT population). For subjects with multiple events, only the first occurrence will be used in each relevant incidence summary.

For various medical events, including the primary endpoint, detailed definitions of new onset of events are defined in the following table, Table 3.5-1. For medically attended LRTI (regardless RSV Yes or No, or Protocol-defined Yes or No) the total number of event occurrences for each subject and the percentage of each outcome will be summarized by treatment group on 3 time-intervals: Day 150 post dose (on the ITT population), after 150 days post dose (on the ITT population with Day 151 visit), and through 360 days post dose (on ITT population). In addition, a listing that provides relevant information for subjects with more than one medically attended LRTI event throughout the study will be generated. The listing contains the following information: Age at randomization, Hemisphere, Total number of events, Days post dose, AE verbatim term, Date of AE onset/stop, Days from previous event, Visit setting, Protocol-defined (Y/N), RSV (Y/N), and RSV subtype (when applicable).

Table 3.5-1 Definition for New Onset of Events

Event	Description
New onset medically attended RSV LRTI	A new onset medically attended RSV LRTI will be defined as an adverse event (AE) (for which at least one healthcare visit is associated with RSV LRTI) and occurs at least 14 days (and similarly using 30 days) after the resolution date of the previous AE for a medically attended RSV LRTI.
New onset RSV LRTI hospitalization	A new onset medically attended RSV LRTI hospitalization will be defined as an AE (for which at least one hospitalization is associated with RSV LRTI) and occurs at least 14 days (and similarly using 30 days) after the resolution date of the previous AE for a medically attended RSV LRTI hospitalization.
New onset medically attended RSV outpatient LRTI	A new onset medically attended RSV outpatient LRTI will be defined as an AE (for which at least one healthcare outpatient visit is associated with RSV LRTI) and occurs at least 14 days (and similarly using 30 days) after the resolution date of the previous AE for a medically attended RSV outpatient LRTI.

Table 3.5-1 Definition for New Onset of Events

Event	Description
New onset medically attended LRTI	A new onset medically attended LRTI will be defined as an AE of LRTI that occurs after the resolution date of the previous AE for a medically attended LRTI.
New onset LRTI hospitalization	A new onset medically attended LRTI hospitalization will be defined as an AE (with at least one hospitalization associated with LRTI) that occurs after the resolution date of the previous AE for a medically attended LRTI hospitalization.
New onset medically attended outpatient LRTI	A new onset medically attended outpatient LRTI will be defined as an AE (with at least one outpatient healthcare visit associated with LRTI) that occurs after the resolution date of the previous AE for a medically attended outpatient LRTI.

AEs associated with all medically attended LRTI will be summarized overall, as well as categorized by the Medical Dictionary for Regulatory Activities (MedDRA) system organ class (SOC) and preferred term (PT). Summaries will be presented through 150 days, after 150 days, and through 360 days on the ITT, ITT with Day 151 visit and ITT populations, respectively.

